Focused lung ultrasound for diagnosing and risk- stratification of patients with COVID-19 symptoms

April 8, 2020
NCT 04327674

Background

COVID-19 is defined as an infectious disease caused by SAR-CoV-2 virus. It results in pneumonia and sometimes respiratory failure. SARS-CoV-2 pandemic has led to massive strain on health care facilities. A large proportion of the population is at risk of COVID-19 and some estimates suggest that up to 15% will need hospitalization. Such number of patients strains the health care system to its maximum as capacity has limitations even in highly developed countries.

Early reports estimate that more than 80% of patients admitted to hospital with COVID-19 have abnormal findings on chest radiographs¹. Thus, imaging seems to be an important part of the diagnostic work-up. In most hospitals however, access to CT-scanning of the thorax of all patients with COVID-19 or with suspicion of COVID-19 is unrealistic due to restricted capacity. Chest radiographs are faster and easier to do, but may require transportation of the patient to the department of radiology which carries a risk of virus spreading in the hospital. On-site chest radiograph is often of such low quality that diagnosis or follow-up will be difficult.

Focused ultrasound examination of the lungs, FLUS, is a diagnostic tool that can show changes in the lung parenchyma due to pneumonia. FLUS is a bed-side examination performed by the physician which results in reduced risk of in-hospital virus contamination. Furthermore, results from FLUS are immediately available to the physician. This allows rapid decision-making which is essential in cases of high patient burdens as seen in the COVID-19 pandemic.

Furthermore, SARS-CoV-2 positive patients with pneumonia may be at higher risk of respiratory failure than those without pneumonia. Identifying patients at high risk can qualify decisions about monitoring level and organization of intensive care resources. Conversely, patient with COVID-19 symptoms but without pneumonic FLUS finding could likely be managed as out-patients. Such a risk-stratification may optimize the allocation of limited healthcare resources and reserve in-hospital capacity to those patients who needs it.

Hypothesis

FLUS can risk-stratify patients with COVID-19 symptoms.

FLUS can predict respiratory failure in patients with COVID-19 pneumonia.

FLUS can diagnose COVID-19 pneumonia with high sensitivity and specificity using PCR-test and chest radiograph as reference.

Aim

To study the ability of FLUS in COVID-19 to predictive respiratory failure.

To study the diagnostic capability of FLUS to find COVID-19 pneumonia.

To study risk-stratifying capability of FLUS in patients with COVID-19 symptoms.

Method

Design

Multicenter prospective cohort study with convenience sampling.

Setting

Emergency departments or internal medicine departments who admit patients with COVID-19 symptoms.

Participants

Patients who have COVID-19 symptoms and require diagnostic testing.

Patients who have a positive SAR-CoV-2 PCR-test and require admission to hospital.

Inclusion criteria

- Patients who are seen in COVID-clinics or emergency departments due to symptoms that require diagnostic work-up to COVID-19.
- Patients admitted to hospital with positive SARS-COV-2 PCR-test and in whom FLUS is performed less than 48 hours after admission.

Exclusion criteria

- Age less than 18 year.
- Former participation in this study.
- Pre-FLUS ventilator support.

Double inclusion

Inclusion in this study will not restrict patient from inclusion in other studies.

Recruitment

Participants are recruited at the local hospital. In Denmark the study is labelled quality assurance and the need for informed consent is thus waived. Local regulations are followed and it is the responsibility of each inclusion site to achieve appropriate regulatory permissions including need for approval from local ethical committees and healthcare authorities.

Variables

Ultrasound variables: FLUS are performed according to ERS guidelines and to Standard of Operating Procedure specific to this study. Film clips are recorded and saved for later evaluation. 14 zones are scanned. Film clips are marked with scanning position (L1, L2...etc.). If the patient is unable to sit, only anterior and lateral zones are scanned. FLUS findings are assessed on the film clips by an observer blinded to other variables. Findings are coded with 1/0 for presence of pneumonia. Moreover, a scoring system is applied:

FLUS findings	Score
Normal FLUS	0
Interstitial syndrome, defined as more than 3 B-lines in a single zone.	1
Diverse B-lines or irregular pleura	
Interstitial syndrome, defined as more than 3 B-lines in a single zone.	2
Confluent B-lines.	
Consolidations (sub-pleurale, lobar, with or without air-bronchograms)	3

Data on FLUS operator: Level of medical degree. Years of experience with lung ultrasound. Completed training in FLUS.

From patient files the following data is extracted:

Patient demographic: Sex, age, height, weight, co-morbidities.

Clinical data on time of admission: Blood pressure, pulse, peripheral saturation, respiratory frequency, temperature, length of illness, list of symptoms, limitation to treatment i.e. not suited or willing to intensive care treatment and intubation.

Data from radiographic diagnostics: Result of chest radiograph, CT or HRCT scanning, if done for clinical reasons. No further review of radiographic examinations is performed. Results given by local radiology department is used.

Microbiological data: Result of SARS-CoV-2 PCR-test from nasal/oral/laryngeal or tracheal samples.

Data from admission: Time of admission. Place of admission. Time of dismissal. Admission to intensive care. Intubation. Time in ventilator. Death, survival. In hospital survival, 14- and 30-days survival.

Endpoints

Primary endpoint: FLUS (binary: positive/negative pneumonia) related to intubation (yes/no).

Secondary endpoints: Relationship between FLUS and SARS-CoV-2 PCR result.

Relationship between FLUS and radiographic findings.

Relationship between FLUS and admission to intensive care (not intubation).

Relationship between FLUS and re-admission (Patient returning to emergency department or COVID-clinic).

Scores of FLUS findings in different zones.

Data management

The study uses convenience sampling as FLUS may not be available at all times. FLUS is performed by the clinician such that only doctors with clinically relevant work are allowed to scan the patient. This minimizes the risk of disease transfer to doctors and reduces the use of protection equipment.

Ultrasound film clips are recorded according to standard operating procedure. Film clips are stored securely, according to local legal regulations. All variables extracted from patient files are stored in an eCRF using REDCap supplied by Aarhus University Hospital.

Every site will have access to enter data in data capture instruments. Access to REDCap is managed by the project steering committee at Aarhus University Hospital.

Data analysis

All data are analyzed in Stata.

Binary endpoints, including primary endpoint, are analyzed using Chi-2 test. Continuous data are assessed for parametric distribution and analyzed with Student's T-test on logarithmic transformed data in case of non-parametric distribution.

Level of statistical significance is set to 5%.

A logistic prediction model will be developed. Dependent variable is intubation. Independent variables are age (continuous), FLUS result (Binary or ordinal), SARS-CoV-2 status (Binary) and peripheral oxygen saturation (continuous).

The data set will be divided in two. One is used for model development and one is used for validation of the model. Geographic external validity is tested. Internal validity is tested with bootstrapping method. Sensitivity, specificity and ROC AUC is calculated.

Sample size

No prior publications are available for sample size estimation.

For the prediction model we wish to include 10-15 events per independent variable, 50-75 events. From early estimations about 20% of admitted patients requiring intubation our estimate is 375-400 participants.

Inclusion period

An end date is set to May 15 2020. If COVID-19 pandemic is ongoing at this time point the study may extent.

Blinding

Ultrasound film clips are analyzed blinded to other variables.

Plan for publication

Data analysis is estimated to end July 1. 2020. Article submission is estimated to October, 2020.

Preliminary data analysis

Available data will be analyzed soon after 15. May.

Ethical considerations

FLUS is without any risk to patients. COVID-19 is an infectious disease and isolation is needed. Contamination during the study needs to be avoided. For this reason, FLUS is only performed by the physicians who are required to see the patient regardless of this study. The ultrasound equipment is cleaned after each examination in accordance with local guidelines.

Legal regulations

In Denmark the study is classified as a quality assurance project. Arrangements and permission to access to patient files in each site is required. According to guidance from the legal office at Region Midt a data management agreement is not needed.

International data agreements are required to data transfer from international sites to Denmark.

All international sites must adhere to local regulation. Responsibility of this is on the international site.

Publication

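### The reference for FLUS diagnostic accuracy combines PCR and chest radiograph by no stated rule, and the only part of it that can show pneumonia is one the protocol partly distrusts

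*Protocol*

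**What the plan says.** The third hypothesis in the protocol's Hypothesis section is that "FLUS can diagnose COVID-19 pneumonia with high sensitivity and specificity using PCR-test and chest radiograph as reference". Diagnostic capability for COVID-19 pneumonia is one of the three aims.

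The Background separates two kinds of film. For departmental films the stated drawback is moving the patient: "Chest radiographs are faster and easier to do, but may require transportation of the patient to the department of radiology". For the bedside alternative it is quality: "On-site chest radiograph is often of such low quality that diagnosis or follow-up will be difficult". On CT it says that "access to CT-scanning of the thorax of all patients with COVID-19 or with suspicion of COVID-19 is unrealistic due to restricted capacity".

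Under Variables, the imaging data are "Result of chest radiograph, CT or HRCT scanning, if done for clinical reasons". The protocol adds that "No further review of radiographic examinations is performed" and "Results given by local radiology department is used". The matching secondary endpoint is only "Relationship between FLUS and radiographic findings", and the PCR result has its own separate secondary endpoint. Data analysis assigns a chi-square test to binary endpoints. Its one mention of sensitivity and specificity closes the text on the intubation prediction model.

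The SAP lists chest film, CT and PCR as separate descriptive variables and contains no analysis of diagnostic accuracy. Neither document gives a rule for combining PCR with film, a rule for FLUS-positive and film-negative patients, a variable for film type, or a role for CT when FLUS and film disagree.

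**The concern.** Sensitivity and specificity mean what they say only if the reference is close to the truth. Here the target is COVID-19 pneumonia. PCR can confirm the infection but not the pneumonia, so that half of the definition rests on the film. The protocol uses the weakness of on-site films as part of its case for FLUS, then names chest radiograph as the yardstick without excluding or marking those films. With no re-reading, a missed pneumonia stays missed.

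At stake is the secondary diagnostic conclusion. A FLUS examination that correctly finds pneumonia could be reported as having poor specificity. Under a different reading of the same sentence it could be reported as having poor sensitivity. The result would depend partly on a rule chosen after the data are seen.

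**Working it through.** **The plan's own figures.** There is none for diagnostic accuracy. The only sample-size figure serves the intubation model (75 events / 0.20 = 375 participants), and nothing below depends on it.

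**Inputs, all assumed.** FLUS sensitivity and specificity are 0.95. Film specificity is 0.95. Film sensitivity S is 0.70, 0.80 or 0.90. Pneumonia prevalence p is 0.30 or 0.50. FLUS and film errors are independent given true status. The protocol says on-site films make diagnosis difficult but gives no miss rate, so poor quality is taken here to mean missed pneumonia.

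**Film alone as reference.** The share of film-negative patients who have pneumonia is

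m = p(1 − S) / [p(1 − S) + (1 − p) × 0.95].

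Apparent FLUS specificity = 0.05m + 0.95(1 − m) = 0.95 − 0.90m.

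| p | S | m | Apparent specificity |
|---|---|---|---|
| 0.30 | 0.70 | 0.090/0.755 = 0.119 | 0.84 |
| 0.30 | 0.80 | 0.060/0.725 = 0.083 | 0.88 |
| 0.30 | 0.90 | 0.030/0.695 = 0.043 | 0.91 |
| 0.50 | 0.70 | 0.150/0.625 = 0.240 | 0.73 |
| 0.50 | 0.80 | 0.100/0.575 = 0.174 | 0.79 |
| 0.50 | 0.90 | 0.050/0.525 = 0.095 | 0.86 |

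The true value is 0.95 in every row.

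**Shared errors.** Take the extreme case: every pneumonia FLUS misses is also missed by film, and false positives coincide fully. Apparent specificity is then [0.05p + 0.95(1 − p)] / [p(1 − S) + 0.95(1 − p)]. At p = 0.50 this gives 0.500/0.625 = 0.80 for S = 0.70, 0.500/0.575 = 0.87 for S = 0.80, and 0.500/0.525 = 0.95 for S = 0.90. Overlap shrinks the loss and, with a good film, removes it.

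**Effect of the missing combination rule.** This is a separate illustration with assumed inputs: 50% COVID-19 pneumonia, 20% COVID-19 without pneumonia, 30% neither; FLUS 0.90/0.90; film sensitivity 0.80; PCR sensitivity 0.90; no film or PCR false positives; independent errors.

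- Film alone: sensitivity 0.90; specificity (0.10 × 0.10 + 0.50 × 0.90) / 0.60 = 0.77.
- PCR AND film: reference-positive 0.50 × 0.80 × 0.90 = 0.36; sensitivity 0.90; specificity (0.14 × 0.10 + 0.50 × 0.90) / 0.64 = 0.73.
- PCR OR film: reference-positive 0.50 × 0.98 + 0.20 × 0.90 = 0.67; sensitivity (0.49 × 0.90 + 0.18 × 0.10) / 0.67 = 0.69; specificity (0.01 × 0.10 + 0.32 × 0.90) / 0.33 = 0.88.

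With film sensitivity 0.60 the three pairs are 0.90/0.67, 0.90/0.65 and 0.68/0.85. The OR rule protects specificity but counts infected patients without pneumonia as diseased, so sensitivity takes the loss. The same FLUS, with true values of 0.90/0.90, looks different under each rule.

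**The case against.** A reader might infer that film is the sole reference and that the plan scores every pneumonia it misses as a FLUS error. The documents do not support that. PCR is named alongside film, and under an OR rule a PCR-positive pneumonia with a negative film is reference-positive. Nor is an accuracy analysis against film written down: the endpoint is a relationship, the test is chi-square, and the SAP has no such analysis. The problem arises only if the hypothesis is tested as worded.

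A reader might also infer that all the films are poor. The quality complaint covers on-site films only, and their share is not given. The Background also cites early reports of abnormal films in more than 80% of admitted COVID-19 patients. That rate is a weighted average of film sensitivity and the assumed 5% false-positive rate, so it needs film sensitivity above 80% in those patients. The 70% rows therefore fit poorly for films overall and are better read as a low-quality scenario.

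Nor do the aims include showing FLUS superior to film, or replacing it.

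Two objections concern the remedy. Negative percent agreement with film is the same number as apparent specificity, so renaming it corrects nothing by itself. And CT/HRCT is done for clinical reasons and read locally, so as a sole reference it would bring selection of its own. Both objections stand, and they limit what the fix can claim.

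What survives is that the reference has no rule, its pneumonia component is partly distrusted by the protocol, and nothing in either document deals with discordant cases.

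**Conclusion.** The concern holds for the diagnostic aim and its secondary endpoints. Under film alone or PCR AND film, pneumonia missed by the film lowers apparent FLUS specificity. The film-alone calculation takes a true 95% to about 84-91% at 30% prevalence and 73-86% at 50%, for film sensitivity 70-90% and independent errors. In the illustration, requiring PCR as well lowers specificity slightly further, because PCR misses are added to film misses. Under PCR OR film the loss moves mainly to sensitivity.

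These are scenario figures. The documents give no film sensitivity, prevalence, share of on-site films or degree of shared error, so the actual bias cannot be derived. The direction is firm only if the film misses pneumonia that FLUS detects. The primary endpoint, FLUS against intubation, does not use the film and is unaffected.

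**What to change.** 1. State in the protocol and SAP how PCR and film form the reference, and what happens when one result is missing or they disagree.
2. Report FLUS against film as positive and negative percent agreement with kappa. Limit the conclusion to agreement with film, and do not judge the high-specificity hypothesis on film alone. It is this limit on the conclusion, not the change of name, that helps.
3. Record whether each film was on-site or departmental, and stratify the agreement results by it.
4. Add a supplementary paired comparison of FLUS and film against CT/HRCT in patients already scanned.
5. Reword the hypothesis to match.

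The cost is wording in both documents, one eCRF field and one extra analysis of data already collected, with no additional imaging. The downside is that the CT/HRCT subset will be small, clinically selected and locally read. It must be described that way and treated as supportive only.

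### The hypothesis of high sensitivity and specificity for COVID-19 pneumonia has no accuracy analysis; the only analysis that reaches it is a chi-square test, which cannot support it

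*Protocol*

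**What the plan says.** The Hypothesis section of the protocol states that "FLUS can diagnose COVID-19 pneumonia with high sensitivity and specificity using PCR-test and chest radiograph as reference". The Aim section has a matching line: "To study the diagnostic capability of FLUS to find COVID-19 pneumonia". The index test exists in binary form, because under Variables "Findings are coded with 1/0 for presence of pneumonia".

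Under Endpoints, the hypothesis becomes two separate secondary items: "Relationship between FLUS and SARS-CoV-2 PCR result" and "Relationship between FLUS and radiographic findings". Under Data analysis, "Binary endpoints, including primary endpoint, are analyzed using Chi-2 test", and the significance level is 5%. The same section ends its text on the logistic model, whose dependent variable is intubation, by saying that sensitivity, specificity and ROC AUC will be calculated. It attaches no pneumonia reference to that sentence.

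In the SAP, PCR, chest radiograph and CT are rows of the descriptive table only. The group comparisons and models use the mean FLUS score against COVID death, intensive care (ITA) admission and ventilator treatment. The SAP does not mention the binary pneumonia reading.

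**The concern.** A hypothesis about high sensitivity and specificity is a statement about the size of two proportions. A chi-square test asks only whether FLUS and the reference are independent. It says nothing about how large either proportion is, and being two-sided it does not say whether the association runs in the right direction.

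The reference is also unsettled. PCR detects infection, whether or not there is pneumonia. A radiograph can show pneumonia but not its cause. A PCR-positive patient without pneumonia counts as a FLUS false negative against PCR, and pneumonia of another cause counts as a correct FLUS finding against the radiograph. The plan does not say which combination of results means COVID-19 pneumonia, or what value counts as high.

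At stake is the diagnostic aim, which is secondary to the primary endpoint of intubation. Followed as written, the plan would give a p-value for a relationship and commit to no estimate of accuracy.

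**Working it through.** **The plan's own figure.** The Sample size section gives 50–75 events at about 20% intubation, and 375–400 participants. Events divided by rate: 50/0.20 = 250 and 75/0.20 = 375. The 375 reproduces; 400 would correspond to 400 × 0.20 = 80 events. The number is built for the intubation model. No prevalence of COVID-19 pneumonia, target accuracy or precision is given, so the values below are assumptions. I use N = 400, the upper end of the plan's range, and suppose that every patient has the reference result.

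**What a significant chi-square shows.** For a 2×2 table with reference-positive counts a (FLUS+) and b (FLUS−), and reference-negative counts c (FLUS+) and d (FLUS−), the uncorrected Pearson statistic is

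X² = N(ad − bc)² / [(a+b)(c+d)(a+c)(b+d)].

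With 50% reference-positive (200 and 200):

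| Sensitivity / specificity | a, b, c, d | ad − bc | X² | p |
|---|---|---|---|---|
| 60% / 50% | 120, 80, 100, 100 | 4,000 | 400 × 4,000² / (200 × 200 × 220 × 180) = 4.04 | 0.044 |
| 40% / 50% | 80, 120, 100, 100 | −4,000 | 400 × 4,000² / (200 × 200 × 180 × 220) = 4.04 | 0.044 |
| 60% / 60% | 120, 80, 80, 120 | 8,000 | 400 × 8,000² / 200⁴ = 16 | 0.00006 |
| 40% / 40% | 80, 120, 120, 80 | −8,000 | 400 × 8,000² / 200⁴ = 16 | 0.00006 |

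A test with no information has sensitivity + specificity = 100%. The first row reaches 110% and is already significant. In that row a positive FLUS moves the probability of a positive PCR from 50% to 120/220 = 54.5%. The second and fourth rows are worse than chance, with the same p-values as their mirror images. The result does not depend on 50% prevalence: at 30%, sensitivity 61% with specificity 50% (expected counts) gives p = 0.043.

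**What estimates would show.** Exact (Clopper–Pearson) 95% intervals for sensitivity with 200 reference-positives are 52.9% to 66.8% at an observed 60%, 33.2% to 47.1% at 40%, and 85.0% to 93.8% at 90%. These separate a poor, an inverted and a good test, which the p-value does not.

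**PCR as the reference for pneumonia.** Let u be the share of PCR-positive patients without radiographic pneumonia. A FLUS that detects exactly the patients with pneumonia has apparent sensitivity 1 − u against PCR. The protocol's Background says more than 80% of admitted COVID-19 patients have abnormal chest radiographs, so u is below 20% for admitted patients, taking an abnormal film as pneumonia. At u = 20%, apparent sensitivity is 1 − 0.20 = 80%. At u = 30%, an assumption that allows for patients who are not admitted, it is 1 − 0.30 = 70%.

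**Who can contribute to specificity.** Specificity against PCR needs PCR-negative patients. The second inclusion route admits only patients who already have a positive PCR, so it adds none.

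**The case against.** The strongest point on the other side is that the protocol does say sensitivity and specificity will be calculated, without naming what they refer to. By position the sentence follows the validation and bootstrapping of the intubation model. If it was meant to cover PCR and radiograph as well, the plan needs to say so, and the reference definition and confidence intervals would still be missing.

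It is also true that a FLUS-by-PCR table yields both estimates directly. The gap is in what the plan commits to analyse and report; the information is not lost. No decision rule depends on these endpoints, and nothing in the documents says that a significant relationship will be presented as proof of high accuracy.

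Some stronger readings are tempting. A reader might infer that the protocol commits to a composite of PCR and radiograph, and that the separate endpoints contradict it. The wording can equally mean each test in turn, and the two separate endpoints fit that. The supportable point is that the reference is undefined. A reader might also infer that a chi-square test is firmly planned for both comparisons. It is assigned to binary endpoints only; radiographic findings are not declared binary, the SAP lists chest radiograph and CT as groups, and the SAP contains no chi-square test at all.

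The SAP does send secondary outcomes to its logistic model, but the outcomes that it names are clinical. A coefficient for the mean FLUS score would not give the sensitivity or specificity of the binary reading in any case.

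**Conclusion.** The point stands as a gap between hypothesis and analysis, and should be corrected. The only analysis that reaches the diagnostic hypothesis is a chi-square test of association. At N = 400 and an assumed 50% PCR-positive, that test is significant at 60% sensitivity with 50% specificity (p = 0.044), and equally so for the mirrored test that is worse than chance. The prevalence and accuracy values are illustrative, but the conclusion does not hang on them: the test measures neither the size nor the direction of accuracy.

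Against PCR alone, a FLUS that is perfect for pneumonia would show 80% sensitivity at the limit implied by the Background for admitted patients, and 70% under the further 30% assumption.

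The documents do not support the broader conclusion that a composite is the one correct reference, or that it would settle the matter. It brings biases of its own, set out with the fix. The primary endpoint is not affected.

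**What to change.** - For the FLUS-versus-PCR and FLUS-versus-radiograph endpoints, replace the chi-square p-value with the 2×2 table and the sensitivity and specificity of the binary FLUS reading, each with an exact 95% confidence interval. Add this analysis to the SAP.
- Estimate accuracy against PCR in patients enrolled through diagnostic work-up. Entry route is not among the variables that the protocol lists, so it has to be recorded.
- State whether the reference is each test in turn or a composite, and give a rule for when a radiograph counts as positive.
- If a composite (PCR-positive and radiograph-positive) is used, report it alongside the single-reference tables, not in their place.
- Report how many patients had no imaging, and state the resulting limitation.

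The cost is some SAP text, a few table rows and one added variable. The statistical downside is larger. Imaging is recorded only if done for clinical reasons, so radiograph-based and composite estimates rest on patients whom clinicians chose to image: verification is partial and the intervals are wider. For scale, an observed sensitivity of 90% has an exact interval of 85.0% to 93.8% with 200 reference-positives (180/200), and 81.2% to 95.6% with 80 (72/80). The protocol's Background also notes that on-site radiographs are often of poor quality, and films are not re-read for the study. Pneumonia seen on FLUS but missed on the film would then count as a FLUS false positive. Under a composite, FLUS would also lose specificity for correctly seeing pneumonia in PCR-negative patients.
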